5.10 Data Management

5.10.1 Data Collection and Storage

Data will be collected by this study team and will be stored in partially protected computerized in locked offices.

5.10.2 Records Retention

Study records will be retained for Geisinger policy for the duration of the study and for 6 years thereafter.

6 SAFETY MONITORING

6.1 Adverse Event Reporting

This study will utilize the NCI Common Terminology Criteria for Adverse Events (CTCAE) version 5.0 for adverse event (AE) reporting. The CTCAE version 5.0 is located on the CTEP website at

http://ctep.cancer.gov/protocolDevelopment/electronic_applications/adverse_events.htm

Clinical adverse events (AEs) will be monitored throughout the study. The date and time of onset and outcome, course, intensity, action taken, and causality to study treatment will be assessed by the study PI. All AEs will be reported to the institutional review board (IRB) per the Unanticipated Problem Policy Definitions

Given the nature and end points of the feasibility part of the study, the PI would report every 3 months to an independent Data Safety Monitoring Board (DSMB) from the Cancer Institute who will review the AE data.

An **adverse event** (AE) is any untoward, undesired, or unplanned event in the form of signs, symptoms, disease, or laboratory or physiologic observations occurring in a person given a drug or test in a clinical study.

All treatment interventions in this study are standard of care.

Radiation Therapy Adverse Events

Acute

Expected adverse events include hair loss, fatigue, and erythema or soreness of the scalp. Potential acute toxicities include nausea and vomiting as well as temporary aggravation of brain tumor symptoms such as headaches, seizures, and weakness. Reactions in the ear canals and on the ear should be observed and treated symptomatically; these reactions could result in short-term hearing impairment. Dry mouth or altered taste has been occasionally reported.

Early Delayed

Possible early delayed radiation effects include lethargy and transient worsening of existing neurological deficits occurring 1-3 months after radiotherapy treatment.

Late Delayed

Possible late delayed effects of radiotherapy include radiation necrosis, leukoencephalopathy, endocrine dysfunction, and radiation-induced neoplasms. In addition, neurocognitive deficits, which could lead to mental slowing and behavioral change, are possible. Permanent hearing impairment and visual damage are rare. Cataracts can be encountered.

Temozolamide side effects are elaborated under drug therapy.

A **serious adverse event** (SAE) is an AE that:

- Results in death.
- Is **life-threatening** (see below).
- Requires inpatient hospitalization or prolongation of an existing **hospitalization** (see below).
- Results in a persistent or significant **disability** or incapacity (see below).
- Results in cancer.
- Results in a congenital anomaly or birth defect.
- Additionally, important medical events that may not result in death, be life-threatening, or require hospitalization may be considered SAEs when, based on appropriate medical judgment, they may jeopardize the subject and may require medical or surgical intervention to prevent one of the outcomes listed in this definition. Examples of such events include allergic bronchospasm requiring intensive treatment in an emergency room or at home, blood dyscrasias or convulsions that do not result in hospitalization, or development of drug dependency or drug abuse.

Life-threatening refers to immediate risk of death as the event occurred per the reporter. A life-threatening experience does not include an experience, had it occurred in a more severe form, might have caused death, but as it actually occurred, did not create an immediate risk of death. For example, hepatitis that resolved without evidence of hepatic failure would not be considered life-threatening, even though hepatitis of a more severe nature can be fatal. Similarly, an allergic reaction resulting in angioedema of the face would not be life-threatening, even though angioedema of the larynx, allergic bronchospasm, or anaphylaxis can be fatal.

Hospitalization is official admission to a hospital. Hospitalization or prolongation of a hospitalization constitutes criteria for an AE to be serious; however, it is not in itself considered an SAE. In absence of an AE, a hospitalization or prolongation of a hospitalization should not be reported as an SAE by the participating investigator. This is the case in the following situations:

- The hospitalization or prolongation of hospitalization is needed for a procedure required by the protocol.

- The hospitalization or prolongation of hospitalization is part of a routine procedure followed by the center (eg, stent removal after surgery). This will be recorded in the study file.

In addition, a hospitalization for a preexisting condition that has not worsened does not constitute an SAE.

Disability is defined as a substantial disruption in a person's ability to conduct normal life functions.

If there is any doubt about whether the information constitutes an SAE, the information is treated as an SAE.

A **protocol-related adverse event** is an AE occurring during a clinical study that is not related to the study treatment but is considered by the investigators to be related to the research conditions, ie, related to the fact that a subject is participating in the study. For example, a protocol-related AE may be an untoward event occurring during a washout period or an event related to a medical procedure required by the protocol.

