2 ABSTRACT

High grade gliomas, particularly glioblastoma, are the most common malignant primary brain tumors in adults(1). Surgical resection, when feasible, offers the best chance of alleviating the mass effect and increasing the likelihood of durable local control. Whether tumors are resected or deemed unresectable, the standard definitive treatment for high grade glioma is involved field radiation with concurrent and adjuvant temozolomide chemotherapy(2). Additional therapy with anti-VEGF therapies(3, 4) and wearable devices such as alternating electric fields(5) have improved progression free and overall survival modestly.

Unfortunately, most patients recur in the region of the primary tumor, ultimately leading to neurological progression and death in a majority of patients(6). One hypothesis for this progression in the region of the primary tumor has been the persistence of resistant clones, including glioma stem cells(7).

Neoadjuvant, preoperative chemo radiation has consistently shown improvements in local disease control or organ preservation in many cancers including head and neck(8), esophageal(9), rectal(10), bladder cancers(11) and sarcomas(12), leading to improvements in overall survival and limb or organ preservation.

Preoperative therapy has not been well studied in resectable glioblastoma. This study attempts to prospectively assess the feasibility and efficacy of preoperative chemoradiation in improving local control, as this is the predominant mode of failure in these patients leading to poor outcomes.

We plan to do this interventional study in two phases using the Simon two-stage Phase II study design(13). Please see section 5.9 on statistical analysis and plan. In the initial stage if there are no more than 3 unanticipated events after 9 patients, an additional 15 patients will be treated in the second stage of this Phase II study. If no more than 9 of the overall 24 patients overall progress in 8 months the study treatment would be considered significant and worthwhile studying in a future randomized phase III study, comparing preoperative study treatment with standard of care post postoperative chemoradiation to evaluate progression free and overall survival as the end point.

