5.4.2 Approximate Duration of Study

We estimate at least 15 patients a year will be enrolled in this study. With further follow-up of at least 26 months from registration to assess the progression free survival, this Phase II study would be completed in 3 years. The end of the study is the last visit of the last subject or end of collection of data from the patient's electronic health record or whichever is last.

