6.3 Unanticipated Problem reporting

[name], the study PI will notify GIRB of all study SAEs in accordance with policy guidelines. If an SAE has not resolved at the time of the initial report, a follow-up report including all relevant new or reassessed information (e.g., concomitant medication, medical history) will be submitted to GIRB. An SAE will be followed until either resolved or stabilized.

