7.3 Data Monitoring Plan

The initial Feasibility Phase of the study may be limited to 10 patients. If 3 or more of these patients experience unexpected toxicities, the study will be discontinued. A data monitoring committee formulated specifically for the study would review the project from the Feasibility Phase to Phase II of the project.

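### Sections 6.1 and 7.3 describe two different monitoring bodies, neither is assigned the stage 1 toxicity stop, and the only stated feed to an independent monitor is a 3-monthly report

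*Combined protocol and SAP*

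**What the plan says.** Under section 6.1, adverse events are followed for the whole study, the PI judges causality, and events go to the IRB as its policy on unanticipated problems defines. For the feasibility part, "the PI would report every 3 months to an independent Data Safety Monitoring Board (DSMB) from the Cancer Institute", which reviews the adverse event data. Section 6.3 adds that the PI "will notify GIRB of all study SAEs in accordance with policy guidelines".

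Section 7.3 opens with "The initial Feasibility Phase of the study may be limited to 10 patients" and continues with the stop: "If 3 or more of these patients experience unexpected toxicities, the study will be discontinued". It then introduces a body described differently from the one in 6.1: "A data monitoring committee formulated specifically for the study would review the project from the Feasibility Phase to Phase II of the project". No meeting schedule or data feed is given for that committee.

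The Abstract states the stage 1 limit in another way: "In the initial stage if there are no more than 3 unanticipated events after 9 patients", a further 15 patients are treated. Section 5.7 lists what counts as stage 1 toxicity, including tumour progression that rules out surgery, failure to complete the neoadjuvant treatment, and a treatment-related surgical delay beyond 6 weeks. It attaches no number to the list. On accrual, section 5.4.2 says: "We estimate at least 15 patients a year will be enrolled in this study".

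**The concern.** The stop in 7.3 is driven by events: it applies as soon as the third patient qualifies. The only stated route by which an independent monitor learns of events is driven by the calendar. The documents do not say who counts the events, who decides whether one was unexpected, who declares the stop, or whether enrolment waits while that is decided.

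The expedited route goes to the IRB, which is neither of the two monitoring bodies, and it is built around serious adverse events. Several 5.7 components can occur without meeting the definition of a serious adverse event in 6.1. A patient who does not complete neoadjuvant treatment, or whose surgery is delayed, may count toward the limit without generating an SAE report.

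At stake is a modest number of patients who could enter a novel treatment sequence after the protocol's own limit has been reached, and a stop that may be applied late or disputed.

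**Working it through.** The plan gives no operating characteristics for the toxicity stop or the reporting interval, so there is no stated figure to reproduce. The error rates in 5.9.2 belong to the non-progression test and do not bear on this point.

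**Inputs from the documents**
- Accrual: 15 patients a year (5.4.2), so 15/12 = 1.25 a month.
- Interval between reports to the DSMB: 3 months (6.1).
- Stop: 3 or more of 10 patients (7.3).
- Surgery: weeks 8 to 12 (5.6).

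**Reports within the feasibility phase.** Ten patients take 10/1.25 = 8 months to enrol. Since 8/3 = 2.7, only 2 or 3 reports fall within that time.

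**Entries after the limit is reached, if action waits for the next report**
- Full interval: 1.25 × 3 = 3.75 patients.
- Average wait of half an interval: 1.25 × 1.5 = 1.9 patients.

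**Simulation.** There were 20,000 runs per scenario, with random (Poisson) accrual at 15 a year, surgery 8 to 12 weeks after entry, and 3-monthly reports starting at a random point. The documents give no toxicity rate, so true rates of 20%, 30% and 40% were assumed. Toxicity was placed either at surgery or evenly between entry and surgery. The counts run from the third qualifying event among the first 10 patients to the next report.

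| Accrual | Mean further entries | 90th percentile |
|---|---|---|
| Continues past patient 10 | about 1.9 | 4 |
| Stops at 10 | 0.4 to 1.1 | 2 to 3 |

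The lower row is smaller because events come some weeks after entry: by the third event, most of the ten have usually been enrolled.

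**Is reaching the limit plausible?** The binomial chance of 3 or more in 10 is 7.0%, 32.2%, 61.7% and 83.3% at assumed true rates of 10%, 20%, 30% and 40%.

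**Does the limit agree across sections?** At exactly 3 events, the Abstract continues (up to 3 in 9) and section 7.3 stops (3 in 10). The Abstract's limit is exceeded at 4 or more of 9, which has chance 0.8%, 8.6%, 27.0% and 51.7% at the same four rates. At 20%, the two rules therefore differ by 32.2% against 8.6%. The terms differ too: the Abstract counts unanticipated events, 7.3 counts unexpected toxicities, and 5.7 has its own list. Nothing states that these are the same thing.

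**The case against.** The strongest reply is that the protection already exists. Section 7.3 gives a number and an obligatory consequence, so it would be wrong to infer that the stop has no trigger. The sentence on the study-specific committee directly follows the stop, and its wording can be read as covering both phases, which would make that committee the natural owner. A reader might infer that it reviews only the transition to phase II, but that is one reading. The two bodies' roles may also be complementary.

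The PI follows events throughout, recruitment is within one health system, and a 3-monthly report does not bar earlier contact. The IRB's policy is not in the documents, so its speed and any power to suspend cannot be judged. A reader might conclude that the PI alone decides whether the limit is reached. The documents give the PI assessment of events and causality, not that decision.

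A reader might also add the patients already between the start of chemoradiation and surgery (15/52 × 8 = 2.3 to 15/52 × 12 = 3.5) to the new entrants and arrive at roughly 4 to 7 exposed. That sum is not supported. Those patients enrolled before the third event, so the reporting gap did not admit them and an enrolment hold would not affect them. At the average wait of 1.5 months (6.5 weeks), no new entrant would have reached surgery.

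These points limit the size of the problem. They do not supply an owner, an event-driven feed to an independent monitor, or a hold on enrolment.

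**Conclusion.** The point holds in a limited form. Two differently described bodies share oversight, neither is assigned the toxicity stop, and the only stated flow to an independent monitor is 3-monthly. IRB reporting does not reliably close the gap, because not every 5.7 event need be an SAE.

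The size is about 2 further entrants on average, up to about 4, if accrual runs on; and about 1 or fewer on average if it stops at 10. Section 7.3 says only that the phase may be limited to 10, and no pause is written, so both cases are open. The figure of 4 is the full-interval expectation rounded up and the simulated 90th percentile, not a strict maximum.

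These numbers assume 15 patients a year, which 5.4.2 gives as a minimum, and they scale in proportion to accrual when enrolment runs on. They also assume that nobody acts on a mandatory stop before the next report, so they describe what the text allows and do not predict what will happen. This is a cheap improvement to patient safety; it does not affect the efficacy analysis.

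**What to change.** 1. Reconcile the stage 1 limit across the Abstract (continue with up to 3 events in 9), section 5.7 (the list of components) and section 7.3 (stop at 3 of 10), and state which events count. This review takes no position on which limit is right, but a named owner cannot apply the rule until there is only one.
2. Name one of the two bodies already planned, in both 6.1 and 7.3, as owner of that rule, and state what the other body does, if it is kept.
3. Send the owner each qualifying 5.7 event when it occurs, whether or not it is an SAE, in addition to the 3-monthly summary.
4. State that new enrolment is held once the reconciled limit is reached, until that body has ruled. With a hold at that moment, further entries fall to 0.

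The cost is wording in the sections named, a few expedited reports, and a possible short pause in enrolment. No new body is needed.

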6.2 Recording and Reporting

A subject's AEs and SAEs will be recorded and reported from the signing of the informed consent form to withdrawal from study or death.

6.3 Unanticipated Problem reporting

[name], the study PI will notify GIRB of all study SAEs in accordance with policy guidelines. If an SAE has not resolved at the time of the initial report, a follow-up report including all relevant new or reassessed information (e.g., concomitant medication, medical history) will be submitted to GIRB. An SAE will be followed until either resolved or stabilized.

7 PROTECTION OF HUMAN SUBJECTS

7.1 Informed Consent

The investigator will provide for the protection of the subjects by following all applicable regulations. The informed consent form will be submitted to the IRB for review and approval. The following conditions would not apply:

- Assent, alteration or waiver of authorization, waiver of consent, waiver of consent, or waiver of documentation of consent
- Subjects who do not have adequate capacity to give consent

Before any procedures specified in this protocol are performed, a subject must:

- Be informed of all pertinent aspects of the study and all elements of informed consent.
- Be given time to ask questions and time to consider the decision to participate.
- Voluntarily agree to participate in the study.
- Sign and date an IRB-approved informed consent form.

7.2 Protection of Human Subjects Against Risks

All the interventions in this study are standard of care. Hence there are no treatment related study related risks. However, there may be unforeseen the risks due to the sequence of treatment which is novel in this study. The purpose of this prospective study is to analyze if sequencing of standard of care makes is safe and could make a favorable difference as it has in other malignancies.

There are always potential risks related to loss of confidentiality (e.g., loss of insurance or employment, etc.) and all standard precautions will be taken to minimize the risks (eg. password protected files, encryption, locked cabinets)

7.3 Data Monitoring Plan

The initial Feasibility Phase of the study may be limited to 10 patients. If 3 or more of these patients experience unexpected toxicities, the study will be discontinued. A data monitoring committee formulated specifically for the study would review the project from the Feasibility Phase to Phase II of the project.

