5 STUDY DESIGN

5.1 Description

We plan to do this interventional study in two phases using the Simon two stage Phase II study design(13). Please see section 5.9 – Statistical methods. Given the novel approach of an existing treatment scheme, this two-stage design allows for safety and efficacy evaluation to proceed to the complete phase II study.

If the median progression free survival (PFS) in this study, meets significance at the completion of this study, it would form the basis to continue as a randomized phase III study with PFS as the primary study objective and overall survival as the secondary objective.

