5.7 Primary Endpoints

Phase II Simon Stage 1: No study related undue toxicity or progression in the first stage patients: Toxicity is defined as: progression precluding surgery, unanticipated neurological decompensation, non-completion of neoadjuvant therapy (other than protocol defined dose adjustments or discontinuation), treatment related delay of > 6 weeks to surgery, and/or major unforeseen surgical complication requiring repeat surgical intervention including other than non-life- threatening infection like meningitis/encephalitis or septicemia.

Phase II Stage 2 (Entire Cohort): Progression Free Survival: defined as MRI defined progression (increasing FLAIR, enhancement, diffusion and or perfusion) 3 months after completion of therapy (to allow for excluding pseudo progression) OR clinical progression with new or worsening neurological symptoms related to the tumor (by MRI or clinical correlation with location) and not due to non-tumor or study related symptoms.

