5.9.1 Statistical Analysis Plan

The Simon two-stage design will be used.

The median progression-free survival of these patients with current standard of care therapy is in the range of 6-8 months (6.9 months in the standard of care). With the proposed trial of surgical resection of the tumor after chemotherapy and radiation the median progression free survival is anticipated to be approximately 11-12 months from subset analysis of available literature and based on prior data on other disease sites. In other words, the 7-month local progression rates is anticipated to decrease from 50% to 25%, or progression free survival improve from 50-75% Due to assessment of unanticipated adverse events with this novel sequencing of established treatment, a Simon two-stage phase II study design would be used to proceed with the study treatment after meeting prespecified events in the initial phase, with goal being to determine whether the new treatment paradigm is sufficiently promising to warrant a major controlled clinical evaluation against the standard therapy

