5.9.2 Statistical Power and Sample Size Considerations

In the Simon two-phase design of this study, if:

p_0 = progression rate of Standard of care = 0.5 (null Hypothesis)

p_1 = Progression after study treatment = 0.25

OR

p_0 = non-progression rate of 0.5

p_1 = non-progression rate of 0.75

With a

Prespecified Type I error rate $\alpha \leq 0.05$

Prespecified Power ≥ 0.8

For non-progression being the response:

The null hypothesis that the true response rate $p_0=50\%$ will be tested against a one-sided alternative. In the first stage $n_1=11$ patients will be accrued. If there are $r_1=6$ or fewer patients responding (i.e. don't progress) in these $n_1=11$ patients, the study will be stopped. Otherwise $n-n_1=14$ additional patients will be accrued to a total of $n=25$. The null hypothesis will be rejected if $r_2+1=17$ or more responses (If >17 of 25 patients do not progress in 7 months) are observed in the ($n=25$) patients. This design yields a type I error rate of 0.05 and a power of 80% when the true response rate (non-progression at 7 months) is $>75\%$.

After completion of 25 patients followed at least for 7 months of the last patient treated, Primary and secondary endpoints will be evaluated and reported.

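### The stop/go rules contradict each other: the Simon design is 9/24 at 8 months in the Abstract but 11/25 at 7 months in Section 5.9.2, and the safety counts in the Abstract and Section 7.3 clash

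*Combined protocol and SAP*

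**What the plan says.** Four places in the current text describe the first-stage decision.

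- **Abstract (Section 2):** "In the initial stage if there are no more than 3 unanticipated events after 9 patients, an additional 15 patients will be treated". That makes 24 in total. The treatment is judged worthwhile if no more than 9 of the 24 progress in 8 months.
- **Section 5.9.2:** 11 patients are accrued first. "If there are $r_1=6$ or fewer patients responding", meaning without progression, the study stops; otherwise 14 more are added, for a total of 25. The null is rejected at 17 or more non-progressors, but the bracket in the same sentence says more than 17. The time point is 7 months. The section states a type I error of 0.05 and power of 80%.
- **Section 7.3:** a feasibility phase that may be limited to 10 patients. "If 3 or more of these patients experience unexpected toxicities, the study will be discontinued".
- **Section 5.7:** "Phase II Simon Stage 1: No study related undue toxicity or progression in the first stage patients". It goes on: "Toxicity is defined as: progression precluding surgery, unanticipated neurological decompensation, non-completion of neoadjuvant therapy", followed by delay to surgery and major surgical complications. It gives no sample size and no threshold.

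Two further passages bear on how these fit together. Section 5.1 says "this two-stage design allows for safety and efficacy evaluation to proceed to the complete phase II study". Section 5.9.1 gives this reason for the design: "Due to assessment of unanticipated adverse events with this novel sequencing of established treatment, a Simon two-stage phase II study design would be used". The Abstract and 5.1 send the reader to Section 5.9 for the detail, but 5.9 contains no toxicity count.

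**The concern.** These are the rules that decide whether the study continues and whether it is declared positive. Two problems follow from the text.

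First, the Abstract and 5.9.2 both claim to describe the Simon design, yet they differ in first-stage size, total size, success cut-off and time horizon. They cannot both be followed, and they need not have the same error rates.

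Second, the Abstract lets the study go on with 3 events, and 7.3 ends it with 3 affected patients. The terms differ (unanticipated events against unexpected toxicities), and so does the unit as printed (events against patients). Neither passage points to the toxicity list in 5.7, which itself adds progression to the endpoint. If 3 of the first 9 patients were affected, the team could cite the protocol for either decision. A rule settled after those events were known would not be prespecified, in a treatment sequence that the protocol itself calls novel.

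**Working it through.** **Inputs.** From 5.9.2: non-progression p0 = 0.50 and p1 = 0.75, one-sided, alpha at most 0.05, power at least 0.80. From the Abstract: 9 then 15 patients, success if 9 or fewer of 24 progress, that is, 15 or more do not. From 7.3: stop at 3 or more of 10. The documents give no toxicity rate, so the rates in step 4 are assumptions.

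**1. The plan's own figure (5.9.2, 17 or more of 25).** Let X11 and X14 be the non-progressors in stages 1 and 2.
P(success) = sum over x = 7 to 11 of P(X11 = x) × P(X14 ≥ 17 − x).
- At p = 0.50: 0.01447 + 0.01708 + 0.01061 + 0.00325 + 0.00038 = 0.0458.
- At p = 0.75: 0.1276 + 0.2293 + 0.2482 + 0.1533 + 0.0421 = 0.8005.
- Early stop under the null: P(X11 ≤ 6) = 0.726. Expected size: 11 + 14 × 0.274 = 14.8.

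The stated 0.05 and 80% are reproduced. A full search shows that this is the Simon optimal design for these inputs.

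**2. The other cut-off printed in 5.9.2 (more than 17, so 18 or more).** The same sum with 18 gives alpha 0.020 and power 0.701. Only 17 or more gives the stated power.

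**3. The Abstract's 9/24 rule at the same rates (assumed to hold at its 8-month horizon).**
- If its first stage is a safety gate that never stops for progression: P(X24 ≥ 15) = 0.154 at 0.50 and 0.945 at 0.75.
- If its events are read as progressions (continue with 6 or more non-progressors of 9): sum over x = 6 to 9 of P(X9 = x) × P(X15 ≥ 15 − x) = 0.099 at 0.50 and 0.815 at 0.75.

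Both exceed the alpha limit of 0.05.

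**4. The two safety counts.** Assume that both terms mean the same thing and that both count patients. The Abstract stops at 4 or more of 9; 7.3 stops at 3 or more of 10. In the same patients the rules disagree if 3 of the first 9 are affected, or if 2 of 9 are affected and the tenth is too:
P(disagree) = P(X9 = 3) + q × P(X9 = 2).

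| Assumed rate q | Stop, Abstract | Stop, 7.3 | Disagree |
|---|---|---|---|
| 5% | 0.001 | 0.012 | 0.0077 + 0.0031 = 0.011 |
| 10% | 0.008 | 0.070 | 0.0446 + 0.0172 = 0.062 |
| 20% | 0.086 | 0.322 | 0.1762 + 0.0604 = 0.237 |
| 30% | 0.270 | 0.617 | 0.2668 + 0.0800 = 0.347 |

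Under this assumption every disagreement runs one way: the Abstract continues and 7.3 stops.

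**5. Do other sections settle it?** Section 5.9.1 refers to prespecified events without listing them. Section 5.7 places toxicity or progression inside Simon stage 1 without numbers. Section 6.1 has an independent board review adverse event data every 3 months, with no numeric rule. Section 7.3 has a study-specific committee review the move from the feasibility phase to Phase II, but gives it no rule that joins toxicity with non-progression.

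**The case against.** A safety stop and a futility stop can coexist, so a reader who infers three mutually exclusive first-stage rules goes too far. That objection stands: 10 patients for toxicity and 11 for non-progression are not in themselves a contradiction. It does not reconcile 9/24 with 11/25, nor the two safety counts.

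Section 7.3, with 6.1 and 8, can be read as a feasibility phase that comes first, and its wording on size is permissive. This is plausible, but 5.7 and the Abstract place the toxicity criterion inside Simon stage 1. The permissive wording covers the number of patients, not the instruction to discontinue. The two monitoring bodies need not conflict either: one reviews adverse events periodically, the other the transition.

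The 3-in-9 clash depends on the assumption in step 4. As printed, the Abstract counts events, so four events in two patients would exceed its limit without triggering 7.3. At a 5% rate the disagreement is about 1%.

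The Abstract's counts may be left over from another design: 9 and 24 with final cut-off 9 match the Simon design for 0.25 against 0.50 (alpha 0.0485, power 0.8055). The match is incomplete, since that design's first-stage cut-off is 2 and the Abstract prints 3. If they are left over, the disagreement figures fall away, but the printed counts still need replacing.

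A reader might also infer that the stated 80% power is wrong because a safety stop would lower it. The documents do not support that: 5.9.2 states power for the efficacy test, and ending a study for toxicity is what a safety rule is for.

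**Conclusion.** The contradiction is in current text and no other section resolves it. The firm part needs no assumption about terms: the Simon design is 9/24 at 8 months in one place and 11/25 at 7 months in another. Only the second, with success at 17 or more, meets the plan's limits. At the plan's rates the Abstract's rule has alpha 0.154 or 0.099, two to three times the limit. The 5.9.2 design itself is sound; its one flaw is the stray cut-off of more than 17.

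The safety clash is conditional. If the two terms are equivalent and count patients, the rules give opposite decisions with probability 0.01 to 0.35 over assumed rates of 5% to 30%. These figures are illustrative. Independently of them, 5.7 gives the stage-1 endpoint no number, and nothing states how the safety and non-progression stops combine. These are stop/go thresholds, so they must be fixed.

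**What to change.** 1. In the Abstract, replace the 9/24 counts and the 8-month rule with the 5.9.2 design: stop at 6 or fewer non-progressors of 11, total 25, 7 months.
2. In 5.9.2, change the bracketed cut-off from more than 17 to 17 or more, which delivers the stated alpha and power.
3. The sponsor and the monitoring body must reconcile the safety passages (Abstract, 5.7 and 7.3) into one rule with one sample size, one unit, one event definition and one threshold. They should state how it relates to the 5.9.2 non-progression stop and to the progression wording in 5.7. No threshold is proposed here.
4. State that the 80% power refers to the efficacy rule alone.

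The cost is a wording amendment. A table of stopping probabilities for the chosen safety rule is optional and would be illustrative. The design in 5.9.2 and its sample size do not change. Waiting for the 7-month first-stage result may pause accrual, but 5.9.2 already implies that.
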